# **SUMMARY AND BACKGROUND**

ADPKD is the fourth most common cause of chronic kidney disease and accounts for 5% of patients with kidney failure [1]. It is the fourth most common cause for end stage renal disease (ESRD) which typically occurs in the sixth decade of life [17]. ADPKD affects more than 600,000 Americans and 12.5 million people worldwide [2].

ADPKD is characterized by the predisposition to cyst formation and enlargement. The progressive development and enlargement of cysts leads to fibrosis of the renal parenchyma and eventually ESRD [1]. The glomerular filtration rate (GFR) remains stable for many decades due to compensatory hyperfiltration. Therefore, it is imperative to utilize alternative prognostic biomarkers to assess progression to end stage renal disease (ESRD).

Due the genetic heterogeneity in ADPKD, there is significant phenotypic variability with regard to progression to ESRD. Therefore, it is critical to use biomarkers to assess patients' risk of progression to initiate early renal protective measures and therapeutics to delay progression. Factors that suggest rapid progression include hypertension onset  $\leq$  age 35, urologic events such as hemorrhagic cysts or infection  $\leq$  age 35, multiple family members with ESRD  $\leq$  age 55, or PKD 1 mutations if genetics are known. Other objective measures of rapid progression include total kidney volume growth  $\geq$  5% per year (on 3 measurements done at least 6 months apart), GFR decline  $\geq$  2.5 ml/min/year over 5 years and Mayo Imaging Classification of Class 1C-1E. The Mayo Imaging Classification is used in patients with "typical" ADPKD in which individuals have bilateral, diffuse cystic disease. It is a validated calculator for measurement of height-adjusted total kidney volume (htTKV) and predicts trajectory of GFR and time to ESRD [1]. At present, Tolvaptan, a vasopressin V2 antagonist, is the only US Food and Drug Administration (FDA) approved drug for slowing progression of ADPKD in individuals at risk for rapid progression. However, Tolvaptan is associated with significant aquaretic effects and requires frequent lab monitoring for liver toxicity, making it challenging to prescribe.

Lifestyle interventions such as ketogenic diet have shown promise in animal models, yet long-term studies in humans are lacking. We propose that ketogenic diet will slow htTKV growth and thus slow disease progression. Furthermore, it may prove beneficial and reduce need for Tolvaptan, which is associated with significant side effects and financial burden or act as an alternative therapy for those who cannot or chose not to take Tolvaptan.

### **Background:**

Autosomal dominant Polycystic Kidney Disease (ADPKD) is the most common genetic cause for ESRD. It is critical to assess individuals at high risk for disease progression in order to implement kidney protective measures early in disease course.

At present, caloric restriction is the only dietary intervention that has shown benefit with regard to disease progression in this unique population [2]. Animal models suggest metabolic reprogramming contributes to cystic epithelial proliferation and cyst growth [4]. The metabolic alteration in the cystic cell epithelia resembles that of cancer cells, known at the "Warburg Effect". Thus, glucose serves as the primary source of fuel in highly proliferative cystic cells, which consequently shift to aerobic glycolysis as opposed to oxidative phosphorylation through the tricarboxylic acid (TCA) cycle. In the former pathway, glucose is preferentially converted to lactate. The glycolytic products shift to anabolic pathways such as the Pentose Phosphate pathway that sustain cell proliferation and growth via reduction in AMP-activated protein kinase (AMPK) and upregulation of mammalian target of rapamycin (mTOR). This was demonstrated in *Pkd1* knockout mice. Furthermore, glucose deprivation led to reduced cystic cell proliferation [8]. Interestingly, 2-deoxyglucose (2DG), a molecule that inhibits glycolysis, restored normal levels of AMPK and acetyl-CoA carboxylase, reducing increase in total kidney volume [9]. Because of decreased glycolytic activity with administration of 2DG, activation of AMPK inhibits mTOR, which downstream inhibits cell proliferation and cyst growth [10].

Oxidative phosphorylation relies on fatty acid oxidation (FAO) for generation of ATP; impaired FAO is another hallmark in the abnormal metabolic pathways of ADPKD and leads to increased mitochondrial damage. In cystic cells, mitochondria no longer function as the energy sources, but supply the intermediates for anabolic pathways [10]. Additionally, glutamine is catabolized to  $\alpha$ -ketoglutarate, which switches the TCA cycle in the opposite direction and produces acetyl-CoA for fatty acid biosynthesis. Mitochondrial function is thought to be mediated by the polycystins. Polycystin-1 (PC-1) and polycystin-2 (PC-2) are membrane proteins encoded by PKD1 and PKD2 genes. From a metabolic standpoint, PC-1 and PC-2 are present in the mitochondria-associated endoplasmic reticulum membranes. Abnormal polycystin proteins in the setting of ADPKD lead to reduced calcium-dependent oxidative phosphorylation and thus switching to the glycolytic pathway [7]. The abnormal pathways are depicted in Figure 1.

[figure not shown]

Figure 1

Animal models have shown slowed disease progression with diet interventions such as fasting and ketogenic diet, meant to diminish available glucose [7]. Metabolic pathways are under investigation as potential targets for both dietary and pharmacologic interventions. Ketosis improves the phenotype in mouse models of ADPKD, including reduction in fibrosis, reduced kidney and cyst size, and improvement in creatinine clearance. The proposed mechanism involves a switch from glucose metabolism to fat oxidation. The switch leads to activation of AMPK and induces peroxisome proliferator activated receptor α (PPARα) [6]. Activation of PPARα increases fatty acid utilization and oxidative phosphorylation [10]. Additionally, ketosis inhibits mTOR (a known modulator of cyst cell proliferation and fluid secretion). B-hydroxy-butyrate (BHB) elevation and ketogenic diet was shown to reduce cysts number and size in rat models [5]. This supports a theory that cystic cells are unable to utilize ketone bodies as a source of energy, and therefore use glucose as their main source of energy [12]. Ketosis inhibits STAT3 signaling to reduce cyst growth and fibrosis [16]. Figure 2 illustrates ketogenic diet effect.

[figure not shown]

Figure 2

STUDY SYNOPSIS	
Title	Feasibility and Efficacy of a Well-Formulated
	Ketogenic Diet in delaying progression of
	Polycystic Kidney Disease in patients at risk
	for Rapid Progression
Study Design	Phase 1 open label single arm dietary
	intervention study
Study Center	The Ohio State University

Primary Objective	Renal MRI (non-contrast) measures of total
	kidney volume to assess disease progression,
	cyst growth/progression, and stiffness/fibrosis
Secondary Objective	Urine microalbumin, eGFR, body mass and
	composition
Number of Subjects	20 patients

Inclusion Criteria	1. Age 18-65 years old
	2. Diagnosis of ADPKD by imaging
	and/or genetic testing
	3. GFR $\geq$ 25 mg/dl
	4. Patients at risk for rapid progression
	of ADPKD: Mayo Class 1C-1E along
	with any other high risk features
	including early decline in GFR,
	hypertension onset $\leq$ 35 years of age,
	urologic events $\leq 35$ years of age,
	PKD 1 truncating mutation and
	PROPKD score of 4 or higher as
	determined by the treating physician
	5. No changes of medications within the
	last three months.
	6. Able to comply with dietary
	intervention
	7. Ability to sign informed consent
Exclusion Criteria	1. Patients currently being treated with
	Tolvaptan
	2. Diagnosed with diabetes.
	3. Pregnancy
	4. Contraindications to MRI
	5. Ketogenic diet within the last three
	months
	6. Severe kidney disease with GFR < 25
	mg/dl
	7. Unable to purchase food for the diet
	intervention
	8. Gastrointestinal disorders that will
	interfere with diet intervention
	9. Chronic alcohol or drug abuse

# **Target Population:**

Patients with Class 1C-1E Mayo Clinic Imaging Class by MRI with assessment of high risk to progress to ESRD. This may include early onset hypertension  $\leq$  35 years of age, first urologic

event (hematuria or urinary tract infection)  $\leq$  35 years of age, and/or family history of rapid progression to ESRD by about age 55.

# **Study Duration:**

12 months

#### **OUTCOMES**

**Study Endpoints:** Change in total kidney volume (TKV) from baseline to 1 year to assess disease progression. Change in albuminuria and GFR.

**Primary Objective:** The primary Objective will be to determine htTKV at baseline and 1 year after ketogenic diet intervention.

**Secondary Objectives:** The secondary endpoints will be measurement of GFR and 24-h urine microalbumin.

# RESEARCH STRATEGY

This is a prospective study to determine ketogenic diet effect on htTKV, GFR, microalbuminuria. This is a single-center study of 20 patients with ADPKD and deemed high risk for progression to ESRD. This determined by combination of features of ADPKD and htTKV as assessed by prior computed tomography (CT) or MRI. Patients will be recruited from the Polycystic Kidney Disease (PKD) Clinic at Ohio State University Wexner Medical Center. Enrolled patients will have MRI for htTKV, urinary studies, blood tests at baseline, 6 months, and 52 weeks. Blood for GFR will be assessed three times over the course of the study including baseline, 6 months, and 1 year. Participants will follow ketogenic diet for 52 weeks. The [name] Lab Nutrition Team will manage the ketogenic diet.

#### **METHODS**

# **Description of Ketogenic Diet:**

The goal of the KD will be to achieve a state of nutritional ketosis in each person as defined as blood BHB ≥0.5 mM. Typical BHB in a person consuming a well-formulated KD are between 0.5 and 4 mM. We will target BHB levels of >1 mM in participants in the KD, which are expected to be an order of magnitude higher than concentrations observed at baseline.

Baseline to Week 6: Participants will be provided a personalized ketogenic plan with up to 3 ready-to-eat "ketogenic-appropriate" meals per day and supplemental snacks in order to offset participant food costs, ensure nutrient quality, and facilitate adherence. In addition, natural low-carbohydrate/high-fat snacks, sources of fat, and electrolytes will be provided to meet caloric needs. This may include shelf stable items such as high-quality fats/salad dressings, salmon & sardine packets, jerky, cheese whisps, nuts and seeds. The quantity and content of these provided foods will vary from participant to participant based on caloric needs and personal preference.

Weeks 7-52: Participants will transition to a free-living ketogenic diet. They will be provided ongoing personalized support, coaching, and education by the [name] Lab Team to facilitate dietary compliance.

The ketogenic diet intervention will start after all baseline testing is complete. Each participant may require slightly different levels of coaching depending on their baseline knowledge and individual situation. Thus, the intensity of engagement may vary across participants. The ketogenic diet will follow general principles with the aim to achieve blood ketones >0.5 mM, which will require most participants to consume <50 g/day carbohydrate and ~1.5 g/kg reference weight protein. Fat will comprise the remaining calories with an emphasis on monounsaturated and saturated sources from whole foods. A wide range of foods will be incorporated including non-starchy vegetables, fruits (berries, olives, tomatoes, lemons/limes), meats (beef, chicken, pork, fish, lamb), nuts and seeds, oils (olive, canola, coconut), cheese, butter, cream, eggs, and fatty fish (salmon, sardines). Nutritional ketosis is associated with natriuresis that will lead to sodium and fluid loss if the extra sodium excreted is not compensated by individualized intakes. If untreated, the resultant hypovolemia can manifest in side effects and adrenal stress (often mis-characterized as 'keto-flu') that disrupts body fluid, electrolyte, and mineral status. Thus, slightly higher sodium and potassium intakes are required to offset the natriuresis, which will be achieved through the provision of broth/LMNT electrolyte packs and appropriate food sources and cooking methods.

# MRI Imaging protocol for htTKV:

Patients will undergo investigational Magnetic Resonance Imaging for assessment of Total Kidney Volume at baseline and 1 year of study participation. MRI specific safety screening will be performed by a qualified imaging team member prior to the imaging session. Patients will be prepared for imaging by the imaging team member and imaging will be completed over the abdominal area, imaging will last no more than one hour. Studies will be carried out using FDA approved 0.55T, 1.5T, or 3T MRI units. Imaging sequences will include 2D T2-weighted Turbo Spin Echo and 3D T1-weighted fat-water separated sequences. Intravenous contrast agent will not be administered. Images of the abdomen and kidneys will be analyzed in order to calculate height-adjusted TKV according to established practices of the Mayo Imaging Classification [1].

The presence of pre- and post-treatment MRI and laboratory tests for comparing kidney size is crucial for evaluating the effectiveness of the treatment. However, there is a potential for inter and intra-observer bias in the measurement of kidney size. To address this issue, several steps and strategies can be implemented:

**Standardized Protocols**: Develop standardized protocols for measuring kidney size that all observers must adhere to. These protocols should include specific guidelines for image acquisition, positioning of patients, and measurement techniques.

**Training and Calibration:** We have ensured that that all observers receive comprehensive training on the measurement techniques and protocols, prior to the study. This training includes both theoretical and hands-on components. Additionally, periodic calibration sessions can be organized to minimize observer variability.

Quality Control Checks: We will regularly monitor the quality and consistency of measurements throughout the study. If significant variability is observed, additional training and calibration sessions should be conducted.

Interpretation Guidelines: We have developed clear guidelines for interpreting the MRI and lab results. This can help standardize the assessment of improvement in kidney size, reducing the risk of bias in interpretation.

Documentation and Audit Trails: Maintain detailed documentation of all measurements, protocols, and observer assignments. This information can be audited to ensure compliance and identify any potential sources of bias.

Table 1 | Table of Study Procedures.

	Visit 1	Visit 2	Visit 3	Visit 4	Visit 5	Visit 6
MRI Imaging	X					X
Medical History	X	X	X	X	X	X
Questionnaire						
Vitals and	X	X	X	X	X	X
Physical Exam						
Blood Draw	X	X	X	X	X	X
Body	X	X				X
Composition						
(DXA)						

# **Study Procedures:**

Serological Assessment and Health monitoring

Visit 1(Baseline):

- Record patient's medical history, including extrarenal manifestations
- Medications
- Pregnancy history if applicable
- Vitals
- Physical Exam
- Patients will undergo MRI non-contrast for evaluation of htTKV
- Blood will be drawn for baseline assessment of GFR, urine osmolality, and urine microalbumin to creatinine ratio
- Blood samples will be saved for metabolomics analysis
- Body composition will be assessed by dual-energy x-ray absorptiometry (DXA)
- Finger Stick BHB: Finger sticks will be taken daily in the morning, by the participant to determine ketone and glucose levels in a fasted state. Measurements will be reported daily in RedCap or Qualtrics.

CGM/CKM: Continuous Glucose Monitoring (CGM) and Continuous Ketone Monitoring (CKM) will be performed. This involves applying a sensor patch on the back of the arm to measure metabolites in interstitial fluid. The sensor can capture data for 2-weeks.

#### Visit 2 (6 Weeks):

- Same procedures in visit 1, except no MRI will be done at this visit.

### Visit 3 (3 months):

- Same procedures in visit 1, except no MRI or DXA Scan will be done at this visit.

# Visit 4 (6 months):

- Same procedures in visit 1, except no MRI will be done at this visit.

Visit 5 (9 months):

- Same procedures in visit 1, except no MRI or DXA Scan will be done at this visit.

Visit 6 (12 months): Same procedures in visit 1.

- Medications
  - Vitals
- Physical Exam
- Patients will undergo MRI non-contrast for evaluation of htTKV
- Blood will be drawn for assessment of GFR, urine osmolality, and urine microalbumin to creatinine ratio
- Payment of \$500

For testing at the PAES building in the Kinesiology Laboratory, subjects will arrive at the lab in the morning after an overnight fast. We will test for hydration, measure height and body mass, and then have participants complete surveys followed by resting blood pressure. A phlebotomist will obtain blood samples from a forearm vein in subjects after sitting for 10-min. Appropriate sample tubes will be used for EDTA, sodium heparin, or serum for different analytes. A serum tube will be sent to Quest Diagnostics to assess standard chemistry panel (liver enzymes, kidney function, lipids, etc.).

Serum and plasma will be immediately centrifuged and aliquoted into tubes and stored at -80°C until subsequent analyses. Samples will be thawed only once for analysis and assayed in duplicate for ketones, glucose, and insulin, which will be used to calculate an index of insulin resistance, and HbA1c. Extra serum and plasma will be archived for future analysis of biomarkers that may provide insight into novel associations with depression.

We will determine body composition from a single whole-body scan using dual-energy x-ray absorptiometry (iDXA, Lunar Corporation, Madison, WI). Total time for this visit will be approximately 1-2 hours.

#### DATA ANALYSIS AND STATISTICAL METHODS

The study will focus on percent change for TKV, albuminuria, and GFR pre and post the ketogenic dietary intervention. We will collect the following data for each patient including age, sex, race, baseline medications, BMI, albuminuria, GFR, and blood pressure. The univariate analysis will include the above variables and use analysis of variance to assess changes at baseline and at 12 months. Based on the univariate analysis, we will perform linear regression. Ketogenic diet administration will be forced into the model. Other variables will be chosen based on strength of the univariate analysis. Our outcome of interest will be percent change in TKV, albuminuria, and GFR. In regard to MR Imagining, we will utilize a statistical method to account for observer variability. Statistical techniques such as intra-class correlation coefficients (ICC) can quantify the level of agreement between different observers and help correct for any bias.

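### The primary TKV outcome is plain percent change, which equals annual growth only if the scans are exactly 12 months apart, and the protocol does not secure that interval

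*Protocol*

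**What the plan says.** The Data Analysis and Statistical Methods section fixes the outcome scale twice: "The study will focus on percent change for TKV, albuminuria, and GFR pre and post the ketogenic dietary intervention", and again "Our outcome of interest will be percent change in TKV, albuminuria, and GFR". Neither sentence carries a time unit.

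The nominal interval is one year. Under Outcomes the endpoint is "Change in total kidney volume (TKV) from baseline to 1 year to assess disease progression", but the starting point differs between sections:

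- Outcomes, primary objective: "The primary Objective will be to determine htTKV at baseline and 1 year after ketogenic diet intervention".
- MRI Imaging protocol for htTKV: scans "at baseline and 1 year of study participation".

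On the diet itself, Description of Ketogenic Diet says "The ketogenic diet intervention will start after all baseline testing is complete", with no limit on the gap after the baseline scan. Research Strategy says "Participants will follow ketogenic diet for 52 weeks". No section gives a window for the final MRI.

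The Summary and Background section expresses kidney growth per year and lists growth of at least 5% per year as one marker of rapid progression. The synopsis describes a single-arm study.

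**The concern.** Untreated kidneys keep growing, so a longer interval between scans contains more growth and a shorter one less, whatever the diet does. In a randomised trial a common timing shift would largely cancel between arms. Here nothing cancels it: the observed change can be judged only against an expected rate, and the growth mark the protocol offers is per year.

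If final scans run late on average, growth is overstated and a diet benefit is understated; if they run early, the reverse. One late shift follows from the protocol's own wording. If the final scan closes a full 52 weeks of diet, and the diet begins some time after the baseline scan, the scan interval exceeds 52 weeks by the length of that wait.

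**Working it through.** The protocol gives no effect size, standard deviation or power for its 20 patients, so there is no figure of its own to reproduce. The question is how far raw percent change moves when the interval is not 12 months.

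**Inputs.** From the protocol: raw percent change, a nominal one-year interval, a single arm, n = 20, and the mark of 5% per year. Assumed here: untreated growth of 5% per year (range 3% to 8%), a true slowing of 20%, waits of 1 to 3 months, and a between-patient SD of 4 points.

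**Step 1. Scan date off schedule, no diet effect.** Raw change = 100 × [(1 + r)^(months/12) − 1].

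| Interval (months) | r = 3% | r = 5% | r = 8% |
|---|---|---|---|
| 6 | 1.49 | 2.47 | 3.92 |
| 11 | 2.75 | 4.57 | 7.31 |
| 12 | 3.00 | 5.00 | 8.00 |
| 13 | 3.25 | 5.43 | 8.69 |
| 14 | 3.51 | 5.86 | 9.39 |

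One month is worth about 0.25, 0.4 and 0.7 points respectively. At 5%, 0.43/5.00 is about 9% of a year's growth.

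**Step 2. Annualise.** Annualised growth = 100 × [(1 + raw/100)^(12/interval in months) − 1]. At 5% per year with no diet effect this returns 5.00 for every row, so drift in scan dates is removed completely.

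**Step 3. Wait before the diet.** Growth is 5% per year during the wait and 4% per year on the diet (20% slowing). With a 1-month wait and the scan 12 months after diet start:

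- Raw: 1.05^(1/12) × 1.04 − 1 = 4.42%. Apparent slowing is 1 − 4.42/5 = 12%.
- Annualised: 1.0442^(12/13) − 1 = 4.08%. Apparent slowing is 18%.

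With waits of 2 and 3 months, the raw figure shows slowing of 3% and −6%; the annualised figure shows 17% and 16%. If the year runs from the baseline scan, the interval is 12 months, annualising changes nothing, and apparent slowing is 18%, 17% and 15% for waits of 1, 2 and 3 months. The residue is untreated growth inside the interval, which no division by time removes. The choice of starting point therefore matters more than the wait itself.

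**Step 4. Random scatter.** Scan dates scattered with an SD of 1 month add 5 × 1/12 = 0.42 points of SD: √(4² + 0.42²) = 4.02, against 4.00. The loss of precision is negligible.

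**Step 5. Scale against sampling error.** The standard error of the mean is 4/√20 = 0.89 points. A mean shift of one month (0.43 points) is about half of that.

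**Step 6. Choice of formula.** A log rate would give ln(1.05) = 4.88% for growth of 5% per year. The compound form avoids that mismatch with the protocol's mark.

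**The case against.** The strongest reply is that the endpoint already has a one-year base. Outcomes, Study Duration and the procedures table all place the final scan at 12 months, and percent change over one year is percent per year. A reader might infer that the result cannot be set beside the 5% per year mark at all. The documents do not support that: for scans done on schedule the two are directly comparable, and the problem lies only in departures from 12 months.

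Three other strong readings also fail:

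- **A built-in wait of two weeks or more.** Study Procedures says "The sensor can capture data for 2-weeks". That describes what the sensor can do. It does not require a run-in before the diet, and the same list contains continuing daily finger sticks. A wait is possible, but its length is not stated.
- **An expected signal of about 5 points.** The 5% figure marks rapid progression. The protocol states no expected diet effect.
- **Lost precision from variable dates.** Step 4 shows this is trivial. Harm needs a systematic shift, and no section documents one.

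Visit windows and the handling of actual dates are often left to a statistical analysis plan, and one may exist. That argument stands for the missing window taken alone. It does not cover the outcome scale, which the protocol itself states twice, or the two different starting points for the year.

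Annualising also has a cost. A 6-month interval means squaring the volume ratio, which roughly doubles measurement error. The protocol does not specify an early scan, but its withdrawal section asks for observations to be completed as thoroughly as possible, so one could arise.

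**Conclusion.** The point holds as a modest, specific weakness in how the outcome is defined. Raw percent change is correct at exactly 12 months. Away from that, a systematic departure biases a single-arm result by about 0.4 points per month at an assumed growth of 5% per year, with a range of about 0.25 to 0.7 points for 3% to 8%. Whether such a departure will occur, and in which direction, cannot be read from the protocol. What can be read is that nothing prevents it and that the sections disagree on when the year begins.

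Annualising over actual scan dates removes drift in scan dates fully and the effect of a pre-diet wait only in part. The growth rates, the 20% slowing, the waits and the SD of 4 points are assumptions of this review.

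**What to change.** 1. Define the primary TKV outcome as annualised growth, 100 × [(TKV month 12 / TKV baseline)^(1/years between the actual scan dates) − 1], in percent per year. Name both scan dates as data items.
2. Reconcile Outcomes and the MRI section on whether the year runs from the diet or from study participation.
3. Record the diet start date and report the interval from baseline scan to diet start, so that untreated growth before the diet can be seen and allowed for.
4. State that scans taken well before month 12 are down-weighted or confined to a sensitivity analysis.
5. Settle the number of scans: Research Strategy also lists an MRI at 6 months, whereas the MRI section, the procedures table and the visit list give baseline and 12 months only.

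The outcome definition needs no extra visit, scan or patient. The cost is a few sentences and one recorded date, provided this is settled before the data are seen.

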#### **Timing of Monitoring:**

# Monitoring will be conducted at the following time points:

**Baseline:** Prior to enrollment, each participant's medical history, kidney function, and MRI scans will be assessed.

**Regular Intervals:** During the study, participants will be monitored regularly. This includes assessments of dietary adherence (weekly by Key Personnel), vital signs, anthropometrics, blood work and glomerular filtration rate (GFR) will be used for monitoring disease progression at the specified intermediate time points (Baseline, Week 6 and Month 3, Month 6, Month 9, Month 12), and kidney function (Baseline, Month 12 via MRI).

**Adverse Event Reporting:** Any adverse events related to the ketogenic diet or the study protocol will be monitored continuously and reported promptly.

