# **Early Termination:**

We anticipate that participants will follow the diet plan as closely as possible to ensure the study's success. In the event of a more than twofold increase in serum creatinine, reaching Stage II acute kidney injury, we may consider early termination from the study. However, we recognize that individual differences, especially in creatinine levels related to protein intake, may occur. Therefore, decisions about early termination will be made in consultation with a physician. Subsequent visits will involve careful consideration of the rate of increase in serum creatinine, allowing the physician to determine whether continued participation is safe and advisable for the participant's health. Our top priority is the well-being of each participant, and any decisions about early termination will be made with their best interests in mind.

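### The baseline-to-12-month GFR contrast cannot separate an early diet-related shift from a year of decline, and the intermediate GFR values have no role in the analysis

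*Protocol*

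**What the plan says.** Under Data Analysis and Statistical Methods the protocol states: "The study will focus on percent change for TKV, albuminuria, and GFR pre and post the ketogenic dietary intervention". The same section says the univariate analysis will "use analysis of variance to assess changes at baseline and at 12 months". No other time point is mentioned for GFR. The Outcomes section makes GFR a secondary endpoint, and the synopsis lists it as eGFR without naming the marker or equation.

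The diet begins only once baseline testing is finished (Methods, Description of Ketogenic Diet), so the first GFR value is off diet and every later one is on it. That section sets protein at about 1.5 g/kg reference weight. Early Termination accepts that "individual differences, especially in creatinine levels related to protein intake, may occur".

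Two GFR schedules are given:
- **Six values.** Timing of Monitoring says "glomerular filtration rate (GFR) will be used for monitoring disease progression at the specified intermediate time points" and lists baseline, week 6 and months 3, 6, 9 and 12. Study Procedures agrees: Visit 1 includes the GFR draw ("Blood will be drawn for baseline assessment of GFR, urine osmolality, and urine microalbumin to creatinine ratio"), and the later visits repeat Visit 1, for example "Same procedures in visit 1, except no MRI or DXA Scan will be done at this visit" at month 3. Table 1 marks a blood draw at all six visits.
- **Three values.** Research Strategy says GFR is measured three times: at baseline, 6 months and 1 year.

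**The concern.** The 12-month change in GFR is the sum of two things: any shift in eGFR that comes with starting the diet, and a year of disease progression. The protocol acknowledges the first when it discusses stopping individual participants, but makes no allowance for it in the efficacy analysis. With one off-diet value, one on-diet value and no control group, nothing in the stated analysis can tell the two apart. A downward shift would read as faster decline, and an upward shift could hide real decline.

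Under the six-visit schedule, the values that would help are already being collected to follow disease progression, yet the analysis section does not use them.

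**Working it through.** The protocol states no GFR calculation (no effect size, SD, alpha or power), so there is no figure to reproduce. The check works in ml/min rather than percent change.

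**Inputs from the protocol:** N = 20, single arm. Six-visit times in years: 0, 6/52, 0.25, 0.5, 0.75, 1. Three-visit times: 0, 0.5, 1.

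**Assumed, because the documents are silent:** true slope −2.5 ml/min/year (illustrative; the bias does not depend on it); step at diet start −5 to +5 ml/min, constant thereafter; within-patient SD σ of 3, 5 or 8 ml/min; between-patient slope SD τ of 0, 2 or 4 ml/min/year.

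**Bias.** Two-point change = slope × 1 year + step.

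| Step (ml/min) | Two-point change | Straight line through six values | Slope through the five on-diet values |
|---|---|---|---|
| −5 | −7.5 | −5.41 | −2.50 |
| −2 | −4.5 | −3.67 | −2.50 |
| 0 | −2.5 | −2.50 | −2.50 |
| +2 | −0.5 | −1.33 | −2.50 |
| +5 | +2.5 | +0.41 | −2.50 |

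The whole step enters the two-point change. A single straight line through all six values removes only part of it. A model with a separate early segment recovers the slope, provided the step is complete by week 6 and constant afterwards.

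**Precision.** Per-patient slope variance = σ²/Sxx, where Sxx = Σ(t − mean t)². There is only one pre-diet value, so once the early change has its own parameter the later slope rests on the on-diet values alone.

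- Two points (0, 1): Sxx = 0.500, variance 2.00σ².
- Six values, one straight line: Sxx = 0.748, variance 1.34σ².
- Six values, early change separated (five on-diet values): Sxx = 0.520, variance 1.92σ².
- Three values, one straight line: Sxx = 0.500, variance 2.00σ².
- Three values, early change separated (0.5 and 1 only): Sxx = 0.125, variance 8.00σ².

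For 20 complete patients, SE = √[(kσ² + τ²)/20], where k is the multiplier above. With σ = 5 and τ = 2:

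- Two points: √[(2.00 × 25 + 4)/20] = 1.64 ml/min/year.
- Six values, straight line: √[(1.336 × 25 + 4)/20] = 1.37.
- Six values, early change separated: √[(1.922 × 25 + 4)/20] = 1.61.
- Three values, early change separated: √[(8.00 × 25 + 4)/20] = 3.19.

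Over the whole assumed range, the SE relative to two points is 0.82–0.91 for the six-value straight line, 0.98–0.99 with the early change separated, and about 1.6–2.0 for three values with the early change separated.

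The baseline-to-week-6 change is not pure step. It also holds 6/52 of a year's decline, here 2.5 × 6/52 = 0.29 ml/min.

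**The case against.** **The shift is not established.** Early Termination speaks of individual differences when a creatinine rise is being judged, not of a shift across the cohort. No baseline protein intake is given, so even the sign of a mean shift is unknown. This stands: the ±5 ml/min range shows how the contrast behaves and is not a forecast.

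**A small shift would look like rapid progression.** A reader might infer this by comparing a one-off shift with the rapid-decline mark in Summary and Background. That mark is "2.5 ml/min/year over 5 years", a sustained criterion for classifying patients. A single shift within one year is not commensurate with it, and the documents do not support the comparison.

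**Precision is being wasted.** A reader might infer this from 1.34σ² against 2.00σ², a variance one third lower. That gain requires a straight line through all six values, and so no step. Once the step is separated the SE gain is 1–2%. The two complaints cannot both be pressed.

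**The on-diet slope should replace the 12-month change.** This does not follow either. Early Termination treats a creatinine rise as possible kidney injury, so an early change may be real, and demoting the total change could hide it. Total change and later slope answer different questions.

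**The later slope is not clean.** Meals are provided only up to week 6 and the diet is free-living after that, so intake may drift from exactly the point where the second segment begins. This stands as a limit on the remedy.

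**A statistical analysis plan may use the intermediate values.** It may; only the protocol is at hand. But the protocol itself states the baseline-to-12-month contrast, so the point does not rest on an omission.

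**Conclusion.** The point holds as a matter of interpretation for a secondary endpoint. The stated GFR analysis carries any early diet-related shift in full into the 12-month change, and a single-arm design offers nothing to offset it. The size of the distortion equals the size of the shift, which the documents do not give.

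How well the shift can be separated depends on a schedule that the protocol states in two ways. With six values it can be done at essentially the two-point precision (1.92σ² against 2.00σ²). With three values the variance rises fourfold, to 8.00σ². The separation assumes that the early effect is complete by week 6 and stable afterwards. Even then, the later slope has no concurrent comparator and cannot by itself show that the diet slowed decline. The primary kidney-volume result is not affected.

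**What to change.** 1. Reconcile the three-time GFR schedule in Research Strategy with the six-visit schedule in Table 1, Study Procedures and Timing of Monitoring.
2. If six visits stand, amend Data Analysis and Statistical Methods to analyse all eGFR values in a linear mixed model with a patient random effect and a separate early segment from baseline to week 6.
3. Report three quantities side by side, demoting none: the early change, the week-6-to-month-12 slope, and the 12-month change already planned.
4. State that the later slope is uncontrolled and may reflect changes in intake once meals are no longer provided.
5. If only three values will be collected, keep the 12-month change and say plainly that it cannot separate an early shift from decline.

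Cost: under the six-visit schedule, wording and slightly more modelling, with the random-effects structure kept simple at n = 20. No samples or visits are added to that schedule.
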